4.3 Analysis populations

Intent-to-Treat Population (ITT) - All participants who were randomized and completed at least one baseline assessment.

Modified Intent-to-Treat Population (MITT) - The modified intent-to-treat population is defined as all participants in the ITT Population, but excluding those that did not complete at least one treatment period. Analysis will compare relative period effects for PBO and OXY periods on change in scores from Baseline to End of Treatment.

Per protocol Population (PPP) - All participants who completed each protocol specified study visit and who were at least 70% compliant in study drug administration for both treatment periods. For assessments completed by caregiver, the data must be collected within 30 days of last dose of IP. For cognitive outcomes completed by patient, data must be collected within 3 days of last dose of IP. Data for which there are clear validation errors or where administration errors are clear and unreconcilable for neuropsychological testing will also be excluded from PPP. Exclusion for validation errors will only be possible for IRI and RSMS where such validation errors are apparent.

A CONSORT diagram, detailing the participants excluded from each subsequent population restriction will be presented for the study.

Section 5 – Trial Population

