6.2 Analysis Methods

The primary analysis of the change from baseline NPI apathy domain is based on a linear model with covariates for sex and order of treatment in the crossover including data from both Stage 1 and Stage 2 for the target selected treatment arm (ETD) will be used to demonstrate superiority using a nominal 2.5% one-sided test using the PPP. Estimated mean effect of the treatment compared to placebo and 95% confidence intervals will be reported. Analysis will compare relative period effects for PBO and OXY periods via change in scores from Baseline to End of Treatment visit.

Supportive primary analysis will be conducted on the MITT population. Given the crossover design, the ITT analysis excludes those that did not take any study medications in their second treatment period.

Sensitivity analysis combining all dose groups for OXY vs. PBO will be conducted for all primary, secondary, and exploratory outcome measures.

Covariates:

Order of treatment (End of treatment 2: Oxytocin versus End of Treatment 2: Placebo)

Sex (male vs female)

Subgroup analyses:

By sex

By severity

Age (median split : young <67 years; older 67+ years)

Oxytocin Genetic polymorphism (GG vs AG vs AA)

FTD subtype (bvFTD vs PNFA vs SD)

ALL other outcomes as listed above, will be analysed using the same methods as for the primary outcome using 5% 2-sided test. Subject is modeled as a random effect, the others are all fixed effects.

To explore whether hormonal levels or imaging atrophy patterns predict behavioural response to OXY, we will conduct a linear regression with NPI apathy domain change scores for OXY-PBO as the dependent measure and predictors of regional MRI atrophy ratings (scores from the Harper et al. visual rating scale for each of the following regions: orbitofrontal, rostral anterior cingulate, fronto-insula, medial temporal, and posterior), baseline serum estrogen level (continuous), baseline serum testosterone level (continuous), sex, and treatment order.

The following endpoints are included in the prospective analysis plan:

Table 6.1A. Endpoints for Analysis

#	Endpoint	Role	Endpoint Type	Pop	Model

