51	heart rate	Safety Outcome	Continuous < change	miITT	$Y_{\text{period}} = \text{Intercept} + \text{period2} + \text{subject} + \text{female} + \text{OXY}$ For following periods: Y_{period} is HR, change from baseline in each period.
52	Systolic blood pressure	Safety Outcome	Continuous < change	miITT	$Y_{\text{period}} = \text{Intercept} + \text{period2} + \text{subject} + \text{female} + \text{OXY}$ Y_{period} is SBP, change from baseline in each period.
53	Diastolic blood pressure	Safety Outcome	Continuous < change	miITT	$Y_{\text{period}} = \text{Intercept} + \text{period2} + \text{subject} + \text{female} + \text{OXY}$ Y_{period} is DBP, change from baseline in each period.
54	Change in CSF Oxytocin Levels	Exploratory	Continuous	PPP	$Y_{\text{period}} = \text{Intercept} + \text{period2} + \text{subject} + \text{female} + \text{OXY}$ Y_{period} is HR, change from baseline in each period.
55	Adverse Events	Safety Outcome		ITT all dose groups	Counts per OXY and PLC periods, McNemar's test (see below)

56	Serious Adverse Events	Safety Outcome		ITT all dose groups	Counts per OXY and PLC periods McNemar's test (see below)
57	Withdrawal Rate	Safety		ITT all dose groups	Withdrawal counts= ED, EOD, ETD, P
58	Compliance	Safety		ITT all dose groups	Percentage of treatments taken for each dose schedule and period, t-tests

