6.4 Harms

Investigators will assess the occurrence of adverse events and serious adverse events at all patient evaluation time points during the study. All adverse events and serious adverse events, whether volunteered by the patient, discovered by study personnel during questioning, or detected through physical examination, laboratory test, or other means, will be recorded in the patient's medical record and on the appropriate adverse event or serious adverse event eCRF. Each recorded adverse event or serious adverse event will include a description of its duration (i.e., start and end dates), severity, seriousness according to regulatory criteria, if applicable, and suspected relationship to the investigational product, as well as any actions taken. All AEs will be recoded into terms using MEDdra. Type and overall frequency of adverse events under each intervention will be described and analyzed using McNemar's test. Concordant and discordant pairs of adverse events and where appropriate, estimates of effect and precision will help to inform the relative safety of the intervention.

Adverse event	No of adverse events
Zero adverse events under either OXY or placebo	
Adverse event observed under placebo but not under OXY	
Adverse event observed under OXY but not under placebo	
Adverse event observed under both OXY and placebo	

November 23, 2023

Signature: PI [name]

Date

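### Adverse events are compared with McNemar's test in an ITT set that can hold participants treated in one period only; sections 4.3 and 6.2 conflict on whether they belong, and the 6.4 table has no line for them.

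*SAP*

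**What the plan says.** SAP section 6.4 (Harms): "Type and overall frequency of adverse events under each intervention will be described and analyzed using McNemar"'s test. It adds that "Concordant and discordant pairs of adverse events and where appropriate, estimates of effect and precision" will inform relative safety. The table shell there has four rows, including "Zero adverse events under either OXY or placebo" and "Adverse event observed under OXY but not under placebo". Each row presupposes that the participant was observed under both treatments.

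Table 6.1A, rows 55 (adverse events) and 56 (serious adverse events), in section 6.2: the population is ITT with all dose groups, and the analysis is "Counts per OXY and PLC periods" with McNemar's test.

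Section 4.3 defines ITT as "All participants who were randomized and completed at least one baseline assessment". No treatment period has to be completed. The narrower MITT set requires only one completed period.

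Section 6.2, in the text on the primary analysis: "the ITT analysis excludes those that did not take any study medications in their second treatment period".

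Section 5.2 does not allow replacement of withdrawn participants and keeps the data already collected from them. Section 6.3 assumes data missing at random, within models that use every observed value. Section 4.1 sets safety tests at two-sided 5%.

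**The concern.** McNemar's test compares the two discordant cells (event on oxytocin only, event on placebo only) among people observed under both treatments. A participant who stops in period 1 has no second outcome. The SAP does not say how that participant enters the test, and its two statements about ITT point in different directions.

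Two ways of running the test are open to a programmer, and neither answers the stated question about relative safety:

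- **Complete pairs**, which the 6.2 sentence points to if it is carried over to harms. The comparison is limited to people who reached period 2, so an event that ended participation in period 1 is not counted in the test.
- **Untreated period scored as no event**, which the row labels permit. The comparison becomes event risk multiplied by the chance of having received the treatment.

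Events that stop treatment matter most in a harms comparison, and they are the events that separate the two approaches.

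**Working it through.** The SAP states no event rate, stopping rate or power for harms, so there is no plan figure to reproduce. The inputs from the SAP are 60 + 40 = 100 participants (section 4) and two-sided 5% (section 4.1). All event and stopping rates below are assumptions. Periods are taken as independent, with 50 participants per order.

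**1. The same data can give two answers (exact McNemar).** Suppose the complete pairs hold 14 oxytocin-only and 8 placebo-only participants, and 6 more had an oxytocin event in period 1 and stopped.
- Dropped: 14 v 8, p = 0.286.
- Scored as oxytocin-only: 14 + 6 = 20 v 8, p = 0.036.

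**2. Direction of bias with equal risks.** Take a 50% event risk on both treatments, with 40% of period-1 oxytocin events ending participation and none on placebo.
- Expected stoppers: 50 × 0.5 × 0.4 = 10, which leaves 40 oxytocin-first and 50 placebo-first participants.
- Dropped: oxytocin risk among the 40 is (0.5 × 0.6)/0.8 = 0.375. The difference is [40 × (0.375 − 0.5) + 50 × 0]/90 = −0.056.
- Scored as no event: 0.50 − 0.5 × 90/100 = +0.05.
- Simulated false rejection (4,000 replicates, exact test): 9.7% dropped and 7.9% scored, against 3.8% with no stopping.

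**3. Power on complete pairs.** Risks are 12% oxytocin v 2% placebo, with period-1 events ending participation equally often on either treatment. Expected oxytocin-only pairs with no loss: 100 × 0.12 × 0.98 = 11.8. If every period-1 event ends participation, only placebo-first participants contribute: 50 × 0.98 × 0.12 = 5.9.

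| Period-1 events that end participation | 12% v 2%, uncorrected | 12% v 2%, exact | 20% v 5%, uncorrected |
|---|---|---|---|
| none | 82% | 75% | 92% |
| half | 69% | 58% | 82% |
| all | 51% | 31% | 62% |

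(8,000 replicates.) A Mantel-Haenszel test stratified by period, on all exposed participant-periods, keeps 82% (12% v 2%) and 90% (20% v 5%) in the last row. At 10% stopping, complete-pair power at 12% v 2% is 80% against 81% with no loss in one run, and 81% against 83% in another.

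**4. Scoring the untreated period as no event, equal risks, withdrawal unrelated to events.** With 30% period-1 withdrawal on oxytocin and 5% on placebo, 50 + 50 × 0.95 = 97.5 people receive oxytocin and 50 + 50 × 0.70 = 85 receive placebo. At 50% risk on both, the scored risks are 0.4875 and 0.425, an apparent difference of 0.0625 where the true one is zero.

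| Withdrawal, oxytocin v placebo | False rejection, 50% risk | False rejection, 70% risk |
|---|---|---|
| 10% v 5% | 4.8% | 6.0% |
| 20% v 5% | 8.8% | 12.1% |
| 30% v 5% | 13.7% | 24.5% |

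The stratified test on exposed periods stays at 4–5% in the 20% and 30% rows. At 20% v 5% withdrawal with only 10% event risk, scoring gives 5.7%.

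**The case against.** **The SAP does not say that untreated periods are scored as event-free.** A reader might infer this from the row labels in 6.4, but those are only a table shell. Section 6.3, which relies on observed data, leans against it, although McNemar's test is not a model of that kind. This stands: it is a possible reading, not a stated rule.

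**The 6.2 sentence already points to complete pairs, where McNemar's test is well defined.** This stands in part. The sentence is written for the primary efficacy analysis, contradicts the 4.3 definition, and would take everyone stopped in period 1 out of the harms test.

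**The effects can be small.** This stands. Large power losses need half or more of period-1 events to end participation. If events end participation equally often on both treatments, complete-pair McNemar keeps its type I error and only loses power. Scoring as no event costs almost no power at 12% v 2% even when every period-1 event ends participation (82% against 83%). Its false rejections need unequal withdrawal or stopping.

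**Treatment-stopping harms do not vanish from the report.** A reader might infer that they do, but rows 55 and 56 also give counts by treatment period, row 57 reports withdrawals, and section 5.2 keeps the data collected. Only the test is affected, and no decision rule rests on it.

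**Exposed-period methods have weaknesses too.** A Wald logistic GEE gave 67% power with no loss at 12% v 2%, and 62% with full event-driven stopping. With correlated periods and stopping driven only by oxytocin events, its false rejection was 6.6–7.8%. This is why the fix names a stratified test and keeps a model as a check.

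**Conclusion.** The point holds as a conflict that should be resolved. Rows 55 and 56 assign a paired test to a set that, by its own definition, can contain unpaired people; section 6.2 contradicts that definition, and the table cannot hold them. It goes beyond missing detail, because two analysts who both follow the SAP could report different p-values from the same data (0.286 and 0.036 in the example above).

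The effect is small when few events stop participation and withdrawal is similar on both treatments. It becomes material when stopping is common (power 82% down to 51% in the extreme case) or unequal (false rejection up to 24.5% when untreated periods are scored as event-free). These figures rest on assumed rates and independent periods. The documents do not support a claim that the harms comparison will in fact be badly wrong, or that McNemar's test is invalid for participants exposed in both periods.

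**What to change.** In section 6.4 and Table 6.1A rows 55 and 56:

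1. State that the second-period exclusion in section 6.2 does not apply to these rows, so that the population agrees with section 4.3.
2. In each period, compare the proportion of participants with an event among those who took at least one dose in that period, oxytocin against placebo, with a Mantel-Haenszel test stratified by period (exact version when events are sparse).
3. Report participants with an event over participants exposed to each treatment.
4. Keep McNemar's test as a supplementary analysis of participants exposed in both periods.
5. Add two lines to the 6.4 table, for participants exposed to oxytocin only and to placebo only, with their events.

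The cost is SAP wording and a little programming; no new data are needed. The downside is that the comparison is no longer purely within-participant, and the stratified test ignores correlation between a participant's two periods. A cluster-robust or penalised model can serve as a check where event counts allow.
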